16.6.3. Efficacy

HIV-1 RNA <small>CCI</small>
Target Detected / Target Non-Detected/ Super Low Viral Load Testing

 When a measurement of plasma HIV-1 RNA is below the limit of quantification (i.e. 40 c/mL) and is qualitatively observable that will be denoted as a "Target Detected" measure, while HIV-1 RNA below the limit of quantification that is not qualitatively observable that will be denoted as "Target Not Detected". Any measurements <40 c/mL characterised as "Target Not Detected" or "Target Detected" will be captured in the database. SuperLow viral load will also be tested by BioMONTR Labs for viral loads below the limit of quantification at Day 1 and Month 11/12.
Confirmed Virologic Failure

 The definition of CVF is provided in the Protocol, Section 7.1.6 – Definition of Protocol-Defined Virologic Failure
Treatment (TRDF) and Efficacy Related (ERDF) Discontinuation = Failure

 The analysis of time to confirmed virologic failure (CVF) or discontinuation due to treatment related reasons (i.e., drug-related AE, intolerability of injections, protocol defined safety stopping criteria, or lack of efficacy) will censor participants who have not met CVF criteria and are ongoing in the study, or who have discontinued for reasons other than those related to treatment. This will be the Treatment Related Discontinuation = Failure (TRDF) data.

HIV-1 RNA

- Participants who have not met CVF criteria and are ongoing in the study, or who have discontinued for reasons other than lack of efficacy, will be censored in the analysis of the Efficacy Related Discontinuation = Failure (ERDF) data.
- Proportion of Participants without virologic (ERDF) or tolerability (TRDF) failure will be estimated using the Kaplan-Meier nonparametric method based on the time to ERDF or TRDF. The estimated proportion at time point of interest will be presented by treatment group, along with estimated difference in proportions between treatment groups and its associated two-sided 95% CI. The estimate of the standard error used to derive confidence intervals will be based on Greenwood's formula [Kalbfleisch, 1980].
- See [Appendix 10: Variables Defined for Time to Event Analysis](#) for additional details.

CCI

Delay in IP Injection

IM dosing is expected to occur every 2 months starting from the third injection and onwards. The Delay in IP injection (days) will be calculated as:

For the second injection:

$$\text{Delay in IP injection(days)} = \text{Injection date} - \text{date of preceding injection} - 31$$

For other injections:

- $\text{Delay in IP injection(days)} = \text{Injection date} - \text{date of preceding injection} - 62$

Delay in IP injection will be grouped into: ≤ 1 , 2-3, 4-7, >7 days.

- The proportion of participants with HIV-1 RNA ≥ 50 c/mL at Month 12 will be summarized by last delay in IP Injection. The last delay in IP injection will be the delay in IP injection at Month 11(D2I) or Month 12(OLI), or the delay in last IP injection prior to Month 11/Month 12 if a participant does not receive their Month 11/12 injection (i.e. missing visit or withdrawal).
- Delays are defined as more than 31 or 62 days for the second and the subsequent injections, respectively.
- If there are subjects who did not receive any injection or received only one injection, then add the "No injection or only 1 injection" category.

16.6.4. Safety

Adverse Events																							
DAIDS Grading																							

 Clinical adverse events will be graded based on the Division of AIDS Table for Grading the Severity of Adult and Pediatric Adverse Events Version 2.1, March 2017, as specified in the protocol Appendix 4. 																							
Potential QTc Interval Prolonging Events of Interest																							

Potential QTc Interval Prolonging Events of Interest will be identified based on Standardised MedDRA Query (SMQ) for Torsade de pointes/QT prolongation, broad (MedDRA). The terms per this reference are listed below.
 
  
 AE preferred term	
   
Electrocardiogram QT interval abnormal	
 
Electrocardiogram QT prolonged	
 
Long QT syndrome	
 
Long QT syndrome congenital	
 
Torsade de pointes	
 
Ventricular tachycardia	
 
Cardiac arrest	
 
Cardiac death	
 
Cardiac fibrillation	
 
Cardio-respiratory arrest	
 
Electrocardiogram repolarisation abnormality	
 
Electrocardiogram U wave inversion	
 
Electrocardiogram U wave present	
 
Electrocardiogram U-wave abnormality	
 
Loss of consciousness	
 
Sudden cardiac death	
 
Sudden death	
 
Syncope	
 
Ventricular arrhythmia	
 
Ventricular fibrillation	
 
Ventricular flutter	
 
Ventricular tachyarrhythmia	
  
	AE preferred term	Electrocardiogram QT interval abnormal	Electrocardiogram QT prolonged	Long QT syndrome	Long QT syndrome congenital	Torsade de pointes	Ventricular tachycardia	Cardiac arrest	Cardiac death	Cardiac fibrillation	Cardio-respiratory arrest	Electrocardiogram repolarisation abnormality	Electrocardiogram U wave inversion	Electrocardiogram U wave present	Electrocardiogram U-wave abnormality	Loss of consciousness	Sudden cardiac death	Sudden death	Syncope	Ventricular arrhythmia	Ventricular fibrillation	Ventricular flutter	Ventricular tachyarrhythmia
AE preferred term																							
Electrocardiogram QT interval abnormal																							
Electrocardiogram QT prolonged																							
Long QT syndrome																							
Long QT syndrome congenital																							
Torsade de pointes																							
Ventricular tachycardia																							
Cardiac arrest																							
Cardiac death																							
Cardiac fibrillation																							
Cardio-respiratory arrest																							
Electrocardiogram repolarisation abnormality																							
Electrocardiogram U wave inversion																							
Electrocardiogram U wave present																							
Electrocardiogram U-wave abnormality																							
Loss of consciousness																							
Sudden cardiac death																							
Sudden death																							
Syncope																							
Ventricular arrhythmia																							
Ventricular fibrillation																							
Ventricular flutter																							
Ventricular tachyarrhythmia																							
Laboratory Parameters																							

 If a laboratory value which is expected to have a numeric value for summary purposes, has a non-detectable level reported in the database, where the numeric value is missing, but typically a character value starting with '<x' or '>x' (or indicated as less than x or greater than x in the comment field) is present, the number of significant digits in the observed values will 																							

be used to determine how much to add or subtract in order to impute the corresponding numeric value. If a character value starting with “<=x”, then the numeric value will be x.

- Example 1: 2 Significant Digits = ‘< x’ becomes x – 0.01
- Example 2: 1 Significant Digit = ‘> x’ or ‘>=x’ becomes x + 0.1
- Example 3: 0 Significant Digits = ‘< x’ becomes x – 1

Estimate of Glomerular Filtration Rate (GFR) (Levey, 2012)

- Chronic Kidney Disease Epidemiology Collaboration (CKD-EPI) equation [Levey, 2012]. be used by the central laboratory to provide an estimate of GFR, in mL/min per 1.73 m², as follows:

$$GFR = 141 \times \min\left(\frac{CRT_{mg/dL}}{\kappa}, 1\right)^\alpha \times \max\left(\frac{CRT_{mg/dL}}{\kappa}, 1\right)^{-1.209} \times 0.993^{Age} \times [1.018 \text{ if Female}] \times [1.159 \text{ if Black}]$$

Abbreviations / Units:

eGFR (estimated glomerular filtration rate) = mL/min/1.73 m²

age = years at time of assessment

κ = 0.7 (if female) or 0.9 (if male)

α = -0.329 (if female) and -0.411 (if male)

min() = the minimum of CRT/κ or 1

max() = the maximum of CRT/κ or 1

CRTmg/dL = serum creatinine concentration in mg/dL. The serum creatinine concentration in mg/dL is obtained from GSK standard units of μmol/L as CRTmg/dL =0.0113x CRTμmol/L.

Lab Toxicities

- Toxicities will be based on the Division of AIDS (DAIDS) grading system, Version 2.1, March 2017, as specified in the protocol of Appendix 4. Toxicity grades provided by the central laboratory do not distinguish between abnormally high or low criteria, when both are relevant for a particular parameter.
- When summarising toxicity grades for such parameters, they will be categorised as to whether they are above or below the midpoint of normal range.

Parameter	Below Midpoint for those ≥Grade 1	Above Midpoint for those ≥Grade 1
Fasted glucose	Hypoglycemia	Hyperglycemia
Sodium	Hyponatremia	Hypernatremia
Potassium	Hypokalemia	Hyperkalemia

National Cholesterol Education Program (NCEP) Lipid Categories

- In addition to DAIDS toxicity grades (see protocol), lipid values will be categorized according to the 2001 NCEP Adult Lipid Guidelines [Grundy, 2001]

Parameter	Value Range (mmol/L)	Value Range (mg/dL)	Category
Triglycerides	<1.70	<150	Normal
	1.70 to <2.26	150 to <200	Borderline High
	2.26 to <5.65	200 to <500	High
	≥5.65	≥500	Very High
Total Cholesterol	<5.18	<200	Desirable
	5.18 to <6.21	200 to <240	Borderline High
	≥6.21	≥240	High
HDL Cholesterol	<1.04	<40	Low
	1.04 to <1.56	40 to <60	Normal
	≥1.56	≥60	High
LDL Cholesterol	<2.59	<100	Optimal
	2.59 to <3.37	100 to <130	Near/Above Optimal
	3.37 to <4.14	130 to <160	Borderline High
	4.14 to <4.92	160 to <190	High
	≥4.92	≥190	Very High

Total Cholesterol / HDL Cholesterol Ratio

- When both total cholesterol and HDL cholesterol results are available from the same date for a participant, then the ratio will be calculated by dividing the total cholesterol result by the HDL cholesterol result. The ratio can be classified as follows:

Parameter	Value Range
Total Cholesterol / HDL Ratio	< 3.5
	3.5 to < 4.4
	4.4 to < 5
	≥ 5

Percentage change for lipids	
The percentage change from Baseline* is calculated as: $\% \text{ Change from BL} = \frac{\text{Value at Month X} - \text{BL value}}{\text{BL value}} \times 100 \%$	
*Maintenance or Extension	
Other Safety Endpoints	
Extent of Exposure	

 Exposure to CAB+RPV (oral lead-in), CAB LA+RPV LA, BIK will be calculated from the IP eCRF pages. 	
Maintenance Phase: Q2M	
Exposure to CAB + RPV (oral lead-in) = * Q2M OLI subjects only	Oral lead-in CAB/RPV Stop Date – Oral lead-in CAB/RPV Start Date +1
Exposure to CAB LA + RPV LA =	Number of IP injections received during Maintenance Phase up to and include the Month 12 (OLI) or the Month 11 (D2I) injection
Overall Exposure to IP (Q2M OLI) =	min [Date of latest Maintenance Phase visit up to and including Month 14 (OLI), max (Date of last CAB LA + RPV LA injection +67, Date of last oral CAB/RPV dose)] – Oral lead-in CAB/RPV Start Date +1
Overall Exposure to IP (Q2M D2I) =	min [Date of latest Maintenance Phase visit up to and including Month 13(D2I), max (Date of last CAB LA + RPV LA injection +67, Date of last oral CAB/RPV dose)] – CAB LA + RPV LA Start Date +1
Overall Exposure to Study Treatment (OLI) =	min [Date of latest Maintenance Phase visit up to and including Month 14, max (Date of last CAB LA + RPV LA injection +67, Date of last oral CAB/RPV dose, Date of last oral SOC bridging)] – Oral lead-in CAB/RPV Start Date +1
Overall Exposure to Study Treatment (D2I) =	min [Date of latest Maintenance Phase visit up to and including Month 13, max (Date of last CAB LA + RPV LA injection +67, Date of last oral CAB/RPV dose, Date of last oral SOC bridging)] – CAB LA + RPV LA Start Date +1
Maintenance Phase: BIK arm	
Exposure = Min (Date of latest Maintenance Phase visit up to and including Month 13, Maintenance Phase Treatment Stop Date, Date of Maintenance Phase Discontinuation) – Maintenance Treatment Start Date + 1	

 ◦ Last oral dose may be CAB/RPV or SOC ART Oral Bridging where CAB/RPV is not available due to COVID-19 ◦ Last CAB LA + RPV LA injection / last oral dose is only applicable to participants who permanently discontinue from study 	

Corrected QT (QTc)

When not entered directly in the eCRF, corrected QT intervals by Bazett's (QTcB) and Fridericia's (QTcF) formulas will be calculated, in msec, depending on the availability of other measurements.
 
If RR interval (in msec) is provided then missing QTcB and/or QTcF will be derived as
 $QTcB = \frac{QT}{\sqrt{RR/1000}} \qquad QTcF = \frac{QT}{\sqrt[3]{RR/1000}}$ 
where uncorrected QT interval is also measured in msec.
 
If RR interval is not provided directly and one of QTcB or QTcF has been entered, then RR interval can be obtained from the above formulas and used to calculate the other correction method value; i.e.,
 $QTcB = \sqrt{\frac{QTcF^3}{QT}} \qquad QTcF = \sqrt[3]{QT \cdot QTcB^2}$
QTc Values by Category

The following categories for QTc will be used:
 
 • For absolute QTc values: 
 ≤450 >450 to ≤480 >480 to ≤500 >500 • For change from baseline in QTc values: 
 ≤30 >30 to ≤60 >60
Columbia Suicide Severity Rating Scale (C-SSRS) (Posner, 2007)

 • Missing data will not have any imputation performed (Nilsson, 2013)

Homeostatic model assessment-Insulin Resistance (HOMA-IR)

- $\text{HOMA-IR} = (\text{fasting plasma insulin (mU/L)} * \text{fasting plasma glucose (mmol/L)}) / 22.5.$
- HOMA-IR categories will be categorised as follows for the shift table analysis:
 1. <2
 2. 2 to <3
 3. 3 to <4
 4. ≥ 4

All HOMA-IR analyses will be based on fasting values and only patients with post-baseline values will be included in analyses (i.e. patients with missing post-baseline HOMA-IR will not be included in summary tables or figures).

The following subjects will be excluded from the HOMA-IR analysis:

- diabetic as captured on the medical history or have taken an anti-diabetic medication (ATC code "A10" (DRUGS USED IN DIABETES)) up to screening
- fasting glucose >126mg/dl and HbA1C >6.5% at Day 1
- have had a cosmetic procedure including liposuction/liposculpture of the thighs, buttocks, hips and/or abdomen

Metabolic Syndrome

- Diagnosis of Metabolic Syndrome is defined as follows per joint interim statement of the International Diabetes Federation Task Force on Epidemiology and Prevention; National Heart, Lung, and Blood Institute; American Heart Association; World Heart Federation; International Atherosclerosis Society; and International Association for the Study of Obesity.
- Three abnormal findings out of the following five qualifies a person for the metabolic syndrome:
 - Elevated waist circumference
 - Males: ≥ 102 cm (≥ 40 in)
 - Females: ≥ 88 cm (≥ 35 in)
 - Elevated triglycerides
 - ≥ 150 mg/dL (1.7 mmol/L)
 - Reduced HDL-C
 - Males: < 40 mg/dL (1.0 mmol/L)
 - Females: < 50 mg/dL (1.3 mmol/L)
 - Elevated blood pressure (meeting either or both criteria)
 - Systolic ≥ 130 and/or diastolic ≥ 85 mm Hg
 - Elevated fasting glucose
 - ≥ 100 mg/dL

BMI (For Shift Table)

The following categories will be used for BMI shift tables:
 
<Normal: <18.5 kg/m² Normal: 18.5 - <25 kg/m² Overweight: 25 - <30 kg/m² Obese: >= 30 kg/m²

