8.5.2. Metabolic Syndrome

Diagnosis of Metabolic Syndrome is defined as follows per joint interim statement of the International Diabetes Federation Task Force on Epidemiology and Prevention; National Heart, Lung, and Blood Institute; American Heart Association; World Heart Federation; International Atherosclerosis Society; and International Association for the Study of Obesity. Three abnormal findings out of the five risk factors would qualify a person for the metabolic syndrome (waist circumference, triglycerides, HDL, BP and fasting glucose) at each planned time point. See Section 16.6.4 for cutoff details. Percent of subjects diagnosed with metabolic syndrome will be produced. Patient profile as well as listing of clinical diagnosis factors over time may also be provided for those who are diagnosed with metabolic syndrome.

Statistical Analyses
Endpoints

 Proportion of subjects with metabolic syndrome at Month 6 (OLI and BIK)/Month 5 (D2I) and at Month 12 (OLI and BIK)/Month 11 (D2I)
Covariates

 Baseline CD4+ cell count (continuous) Gender at Birth (male, female) Baseline BMI (<30 kg/m², ≥30 kg/m²) Age (35-<50, ≥50, <35 years) Race (White, Black/African American, Other) Smoking Status (Never, Current, Former) Hypertension (Yes vs no) Baseline Triglyceride (High vs. Normal) Baseline HDL (Low, High vs Normal) Baseline HOMA-IR (2 to <3, 3 to <4, ≥4 vs <2) 
Note: Hypertension is defined as having a medical history of hypertension or use of medication treating hypertension (current and past)

Data Handling

 OC (Observed Case) dataset will be used.
Model Specification

 A logistic regression model will be performed on the proportion of subjects with metabolic syndrome at Month 6 (OLI and BIK)/5 (D2I) and at Month 12 (OLI and BIK)/11 (D2I) adjusting for the covariates as above.
Model Checking & Diagnostics

 Upon delivery of data, an assessment regarding the amount of missing data will be made. If the amount of missing outcome data considered as a result of other impacts such as COVID-19 is substantial, the logistic regression analysis may not be performed. If the percent of subjects are below 5% of the total number of subjects (observed data), or if complete or quasi-complete separation is observed in the data, then the analysis may not be performed.

Statistical Analyses

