16.7.2.2. Handling of Missing data for Statistical Analysis

Element	Reporting Detail
Snapshot	
 • In the Snapshot dataset, participants without HIV-1 RNA data in the assessment window for the visit of interest (due to missing data or discontinuation of IP prior to the visit window) do not belong to 'HIV-1 RNA < 50 c/mL (or <200 c/mL)'. The nature of this missing data will be further classified in Snapshot summaries as either 'HIV-1 RNA≥50' or 'No Virologic Data at Week X'. See Appendix 9: Snapshot Algorithm Details.
Lipid Evaluable	
 • For subjects with lipid-modifying agent use, lipid assessments will be considered non-evaluable (equal to missing) after initiation without any imputation. • If participants take lipid modifying agents within 12 weeks prior to the start of the study treatment, all the post-baseline values will be non-evaluable. • The lipid evaluability rules will be used for the following displays: 
 Summary of Fasting TC/HDL ratio Change from Baseline Summary of Fasting Lipids Percentage Changes from Baseline Summary of Chemistry Changes from Baseline • All other displays of lipids (i.e. toxicity tables and NCEP tables) will use observed fasting data, without considering lipid evaluability. • The same rule of "lipid evaluable" will be applied to anthropometric parameters as specified in Section 8.5.3: 
 - Weight, Height and BMI - Waist circumferences - Hip circumference - CCI [REDACTED] - CCI [REDACTED] - Tanita scale parameters (total body fat percent, total body water percent, muscle mass, and bone mineral mass).

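### The metabolic-syndrome derivation uses measured values only, so drug-controlled components count as not met; a treatment-inclusive version should be reported beside it

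*SAP*

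**What the plan says.** Section 2.2 makes change from baseline in the proportion with metabolic syndrome a secondary endpoint. Section 16.6.4 sets the rule: "Three abnormal findings out of the following five qualifies a person for the metabolic syndrome". The findings are sex-specific waist cut-offs, triglycerides "≥ 150 mg/dL (1.7 mmol/L"), sex-specific HDL-C cut-offs (for example "Females: < 50 mg/dL (1.3 mmol/L")), blood pressure "Systolic ≥ 130 and/or diastolic ≥ 85 mm Hg", and "Elevated fasting glucose" at 100 mg/dL or more. None has a treatment clause. Section 8.5.2 takes the status afresh from "waist circumference, triglycerides, HDL, BP and fasting glucose) at each planned time point", on observed cases. It feeds Table 3.64 (percentages), Table 3.65 (Yes/No/Missing shift from baseline) and Table 3.66 (logistic regression).

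Medication enters section 8.5.2 only through a model covariate: "Hypertension is defined as having a medical history of hypertension or use of medication treating hypertension (current and past"). Section 16.7.2.2 sets lipids to missing after a lipid-modifying agent is started, for three listed displays. No metabolic-syndrome table is among them, and the section adds that "All other displays of lipids (i.e. toxicity tables and NCEP tables) will use observed fasting data, without considering lipid evaluability".

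**The concern.** A participant with a large waist, raised glucose, normal lipids and blood pressure of 124/78 on an antihypertensive scores 2 of 5 and is not a case. If the antihypertensive was started after baseline, and pressure was raised before, Table 3.65 shows Yes to No. Disease under treatment then looks the same as disease that has gone.

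Two things are at stake. The percentages and the shift table describe measured status only, so they understate how many participants have the syndrome or are being treated for part of it. And if one arm has more on-study drug starts because its participants worsen more, that arm can look better.

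**Working it through.** **Step 1. How the SAP treats medication elsewhere.**

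| Analysis | Section | Medication taken into account? |
|---|---|---|
| Hypertension covariate | 8.5.2 | Yes, use of a drug defines hypertension |
| Framingham risk, Months 6 and 12 | 16.6.2 | Yes, antihypertensives started up to the time point |
| Lipid changes (three listed displays) | 16.7.2.2 | Yes, values after a lipid drug are missing |
| Waist and other anthropometric summaries | 8.5.3, 16.7.2.2 | Yes, values after a lipid drug are non-evaluable |
| HOMA-IR | 8.5.4, 16.6.4 | Yes, anti-diabetic drugs up to screening exclude |
| Metabolic-syndrome status | 8.5.2, 16.6.4 | No |

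The same on-drug triglyceride value can therefore be missing in Table 3.40 and normal in Table 3.64. The same on-drug waist value can be non-evaluable in Table 3.61 and used in Table 3.64.

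**Step 2. When a flip occurs.** The SAP gives no figure to reproduce, so I counted patterns of the five factors.

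- Qualifying patterns: C(5,3) + C(5,4) + C(5,5) = 10 + 5 + 1 = 16 of 32.
- Qualifying patterns containing one given factor: at least 2 of the other 4, so 6 + 4 + 1 = 11.
- Of these, the diagnosis is lost when that factor normalises if exactly 2 others are abnormal: 6. So 6 of 11 flip.
- Qualifying patterns containing two given factors: at least 1 of the other 3, so 3 + 3 + 1 = 7. If both normalise, only the pattern with all three others survives. So 6 of 7 flip.

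These counts are unweighted.

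**Step 3. Size of the under-count.** The SAP gives no rates, so all inputs are assumptions. Off-drug abnormal rates for waist, triglycerides, HDL, blood pressure and glucose are 35, 30, 25, 35 and 20%, with latent correlation 0.25. The share treated and, among those, the share controlled run from low to high as follows: blood pressure 0.2 and 0.6 to 0.6 and 0.7; triglycerides 0.15 and 0.4 to 0.5 and 0.5; glucose 0.1 and 0.3 to 0.25 and 0.3. By simulation:

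- counting treated criteria: 20.5%;
- as written, low drug use: 18.8%, so 1.7 points or 1.7/20.5 = 8% of cases are missed;
- as written, high drug use: 14.3%, so 6.2 points or 6.2/20.5 = 30% are missed.

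**Step 4. Between-arm effect with no true difference.** Assume antihypertensive starts of 8% against 2% of all participants, all in people with raised pressure, 60% controlled. The extra share normalised is (8 − 2) × 0.6 = 3.6 points. About a quarter of these have exactly two other findings, which gives a spurious difference of about 0.9 points. If the 8% and 2% apply only within participants with raised pressure, it is about 0.3 points.

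For scale, section 2.3 plans about 654 participants at 2:1, so 436 and 218. SE = √[p(1 − p)(1/436 + 1/218)], which is 2.9 points at p = 14.4% and 3.4 points at p = 20.6%. The 0.9 points is about 0.3 SE.

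A more extreme assumption has 5% of cases masked in one arm and 15% to 25% in the other, with true prevalence of 15% to 35%. The spurious difference is prevalence × difference in masking: from 0.15 × 0.10 = 1.5 points to 0.35 × 0.20 = 7.0 points (odds ratio 1.14 to 1.40). With equal masking it is zero.

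**The case against.** Measured status regardless of medication is a legitimate target, and against that target nothing is understated. In an open-label trial drug starts are prescriber decisions made with knowledge of the arm, while measured cut-offs are objective. Randomisation balances baseline medication in expectation. The model adjusts for hypertension including drug use and for baseline triglycerides, HDL and HOMA-IR. Table 3.64 shows each factor separately, Tables 1.21 and 1.22 show concomitant and lipid-modifying drugs, and Listing 56 shows factor values by visit. No decision rule depends on this endpoint.

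Much of this stands. It is a good reason to keep the measured-value version and not replace it. It does not remove the point. The covariates leave the outcome, the percentages and the shift table unchanged. The medication tables are not linked to syndrome status. The Month 12 profile plots (Figures 3.11 to 3.13) are limited to participants who have the syndrome at Month 11/12, so a drug-driven Yes to No would be absent from them.

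The objection also exposes a trap in the repair. If any ATC C10 drug met both lipid criteria, one drug would score 2 of 5 and one further finding would make a case. With the Step 3 rates and 10% to 20% taking such a drug for another reason (assumed), prevalence rises from 20.5% to about 24.0% to 28.4%. That over-count of 3.5 to 7.9 points is at least comparable with the under-count being repaired.

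A reader might infer more than the document supports in three ways. Starting a drug does not always turn Yes into No: the value must fall below its cut-off and fewer than three findings must remain. The between-arm comparison is not shown to be materially biased, because that needs unequal drug starts, on which the SAP has no data. And it cannot be said here that the SAP departs from the joint interim statement it cites, because that source is not at hand.

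**Conclusion.** The point holds in limited form. The derivation ignores drug treatment, unlike the neighbouring analyses in the same SAP, and the SAP does not say that this is intended. Whether the lipid-evaluable rule reaches the syndrome is not stated expressly: the listed displays exclude it, and the sentence on other lipid displays names only toxicity and NCEP tables as its instances.

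The descriptive effect could be noticeable (8% to 30% of treated-or-abnormal cases missed), but only under assumed rates of treatment and control. The between-arm effect is probably small, around 0.3 to 0.9 points in the plausible illustration, and zero if masking is equal. The primary endpoint is untouched. The change is worth making because this is a stated secondary endpoint and the repair is cheap.

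**What to change.** In section 16.6.4, carried into 8.5.2 and Tables 3.64 to 3.66, add a treatment-inclusive classification beside the measured-value one, derived in the same way at baseline and at follow-up:

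- blood pressure: abnormal value or current antihypertensive use;
- glucose: abnormal value or current ATC A10 use;
- lipids: a current ATC C10 drug counts toward at most one lipid criterion, named in advance; the other is judged on its value;
- waist: measured value only.

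State explicitly that the lipid-evaluable rule, for lipids and for waist, does not apply to this derivation, or else apply it consistently.

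The cost is some SAP wording, one derivation and a second version of three tables. Concomitant medications are already collected, antihypertensive use by time point is already derived for Framingham risk, and lipid-modifying agents are already tabulated. The downside is that drugs taken for other indications will be counted, so prevalence will be higher. That is why both versions should be shown.
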